The CDC's initial interim guidelines for dental settings during COVID-19 suggested that using a pre-procedural rinse with an antimicrobial product (such as chlorhexidine gluconate, essential oils, hydrogen peroxide, povidone-iodine, or cetylpyridinium chloride) could have a potential effect in reducing the level of oral microorganisms in aerosols and spatter generated during dental procedures⁷. In April 2020, the CDC and the American Dental Association (ADA) recommended using a mouthwash containing 1.0-1.5% H₂O₂ as a pre-procedural rinse before dental treatment to reduce SARS-CoV-2 load potentially; however, no US clinical studies have been conducted to support this claim.

This study aims to assess the effect of four over-the-counter (OTC) antiseptic mouthwash/gargling solutions compared to a distilled water control on the SARS-CoV-2 load in unstimulated saliva, throat wash (gargle lavage), and oropharyngeal swab samples. Also, study participants will be assessed for the severity of their clinical symptoms during the study period. The 4-week protocol was selected as studies show people with COVID can continue to shed the virus and potentially transmit to the others for a 2- to 4-week period. This study will also examine tobacco use, marijuana smoking, or vaping as possible effect modifiers of antiseptic mouthwash on SARS-CoV-2. Study participants will be followed up daily via a very short daily questionnaire and every 3 months for the next 11 months after the study is finished for longerterm follow-up via text messaging. The null hypothesis of the study is that there is no difference between any OTC antiseptic mouthwash solution (Chlorine Dioxide (ClO₂), Hydrogen Peroxide (H₂O₂), Cetylprydinium Chloride (CPC), Essential Oils (EO), and distilled water (H₂O) in reducing SARS-CoV-2 load in unstimulated saliva, throat wash (gargle lavage), and oropharyngeal swab samples (baseline to 4 week follow-up).

Objectives {7}

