1a. To assess and compare the SARS-CoV-2 viral load in unstimulated saliva and throat wash (gargle lavage) samples before and after rinse at baseline in Chlorine Dioxide (ClO₂), Hydrogen Peroxide (H₂O₂), Cetylprydinium Chloride (CPC), and Essential Oils (EO) groups versus distilled water (H₂O) group (pre-procedural rinse primary outcome measure).1b. To assess the SARS-CoV-2 viral load reduction of throat wash (gargle lavage) samples from baseline to 4 weeks in Chlorine Dioxide (ClO₂), Hydrogen Peroxide (H₂O₂), Cetylprydinium Chloride (CPC), and Essential Oils (EO) groups versus distilled water (H₂O) group solution of throat wash (gargle lavage) samples from baseline to 4 weeks in Chlorine Dioxide (ClO₂), Hydrogen Peroxide (H₂O₂), Cetylprydinium Chloride (CPC), and Essential Oils (EO) groups versus distilled water (H₂O) group (homecare reduction primary outcome measure).

2. To assess the clinical symptom onset progression and health care utilization (e.g. hospitalization) from baseline to 4 weeks comparing Chlorine Dioxide (ClO₂), Hydrogen Peroxide (H₂O₂), Cetylprydinium Chloride (CPC), Essential Oils (EO) to distilled water (secondary outcome measures).

3. To assess if tobacco use, marijuana smoking, or vaping are effect modifiers of primary outcome measures.

4. To evaluate study participants' in a 12-month follow up.

Trial design {8}

This is a single center, 5-arm, parallel groups, double-blinded (participant, outcomes assessor),

randomized controlled trial of adults who are COVID-19 positive using over-the-counter (OTC) mouthwash/gargling solutions: Chlorine Dioxide (ClO₂) (CloSYS Ultra Sensitive, Rowpar Pharmaceutical Inc., USA); Hydrogen Peroxide (H₂O₂) (Oral-B Mouth Sore, Proctor & Gamble, USA); Cetylprydinium Chloride (CPC) (Crest Pro-Health Multi-Protection, Proctor & Gamble, USA); Essential Oils (EO) (Listerine Zero, Johnson & Johnson, USA) versus distilled water as a control.

Methods: Participants, interventions and outcomes

Study setting {9}

Consenting community-dwelling San Francisco Bay Area (California, USA) participants positive for COVID-19.

Eligibility criteria {10}

Inclusion criteria

- Adults 18 years and older
- Tested positive for COVID-19 with a sample collected in the prior 7 days
- Ability to read and speak in English or Spanish
- Ability to participate in the study for 4 weeks
- Ability to gargle
- Not having any oral condition that might worsen with gargling solutions

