- Not having an allergy to a mouthwash ingredient that has been used before
- Not using another mouthwash/gargling solution
- Not taking antimicrobial medications (antibacterial, antiviral (e.g., Truvada), antibiotics including off-label FDA-approved medications such as Remdesivir)

- Have a cellphone and agree to receive text messages for reminders to use mouthwash during the day and for follow-up visits
- Ability to meet with study staff via videoconference (e.g., Zoom, FaceTime, WhatsApp)

Exclusion criteria

- Those who experience severe clinical symptoms which require hospitalization
- Individuals who receive antiviral medications that could potentially affect viral load in their saliva samples
- Pregnancy or lactation for women due to potential aversions to mouthwash solution taste/smell

Who will take informed consent? {26a}

Study Co-PI or a trained bilingual study staff member will confirm the study participants' eligibility based on inclusion/exclusion criteria before obtaining informed consent and the required waiver/authorization form included in supplemental IRB documents.

Additional consent provisions for collection and use of participant data and biological specimens {26b}

The informed consent form (ICF) explains the participant sample collection procedure, lab test, and potential future studies on samples. The ICF explains test results being kept confidential and participants' ability to discontinue the study at any time, without any interference in their COVID-19 related or other health care.

Interventions

Explanation for the choice of comparators {6b}

The comparator control group is distilled water (H₂O) which may help clear microbes from the oral cavity and throat without deactivating SARS-CoV-2 virus. A published randomized clinical

trial and cost-benefit analysis has shown gargling with plain water to be cost effective in reducing URT infections (Sakai et al. 2008). Participants in the control group will be asked to rinse and gargle for 60 seconds with 20ml (4 teaspoons) 4 times per day (including after each meal and before bedtime), for 4 weeks.

Intervention description {11a}

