The study participants should not use any other mouthwashes or take any antimicrobial medication (antibacterial, antiviral, antibiotics including off-label usage such as Remdesivir) during the study. They can continue practicing their usual home oral hygiene care (tooth brushing with a toothpaste, and flossing). If they have a dental emergency (e.g. dental infection such as abscess or pulp infection) they should contact their regular dentist for dental treatments according to their dentist's COVID protocols.

Provisions for post-trial care {30}

The antiseptic mouthwash solutions to be used by study participants are safe over-the-counter solutions that are available without requiring dentist's prescriptions, to improve oral health conditions. Unless individuals might be allergic to the ingredients of the study mouthwashes, they will not face any harm and risks when using the solutions. However, research team will provide their phone numbers and emails if participants confront any problems during the study period. If study participants feel any stress and discomfort due to their COVID-19 status, they will be advised to contact their physician and COVID-19 hotlines as soon as possible to receive required health services. After the study is finished, participants will be asked a few questions by texting a link to an online questionnaire designed in REDCap in about every 3 months over the

next 11 months to see how they are doing, their clinical symptoms, acceptability of using the assigned mouthwash during the trial, and their potential use after the trial.

Outcomes {12}

Primary outcome Measure:

- Change in SARS-Cov-2 viral load: Change in RT-PCR SARS-Cov-2 viral load in unstimulated saliva and throat wash (gargle lavage) samples (Time Frame: Baseline to 4 weeks)

Secondary Outcomes Measures:

- Change in self-reported (questionnaire) clinical symptom onset. A symptom checklist will include: cough, runny nose, scratchy/sore throat, fever, chills, fatigue, muscle ache, shortness of breath, diarrhea/nausea/vomiting, loss of taste/smell, and red /painful eye (Time Frame: Baseline to 4 weeks)
- Change in healthcare utilization and hospitalization (Time Frame: Baseline to 4 weeks) Other Pre-specified Outcome Measures:
 - Change in SARS-Cov-2 viral load in tobacco users, marijuana smokers, or vapers (Time Frame: Baseline to 4 weeks)

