 - Change in self-reported (questionnaire) clinical symptom onset in tobacco users, marijuana smokers, or vapers. A symptom checklist will include: cough, runny nose, scratchy/sore throat, fever, chills, fatigue, muscle ache, shortness of breath, diarrhea/nausea/vomiting, loss of taste/smell, and red /painful eye (Time Frame: Baseline to 4 weeks)
 - Change in healthcare utilization and hospitalization in tobacco users, marijuana smokers, or vapers (Time Frame: Baseline to 4 weeks)

Participant timeline {13}

Study participants will remain in the trial for 4 weeks. After completing the intervention, they will be followed up for the next 11 months via text messaging to ask about clinical symptoms and healthcare utilization, experience using mouthwash, and their interest in using mouthwash after the trial.

Sample size {14}

A total of 150 eligible individuals will be enrolled in the trial after providing informed consent and randomly assigned to 1 of 5 groups. This trial is sized to provide precise estimates of effect size for a future definitive trial with at-risk individuals. However, this trial would be able to detect a rather large effect: a sample size of 24 for a mouthwash group and 24 for the distilled water control group is estimated to have 80% power to detect a 2-fold difference in mean values between the 2 groups with a 2-sided alpha=0.05. Assuming 80% retention through 28 days, 30 participants per group at baseline (150 total) will be enrolled.

Recruitment {15}

Two recruitment routes have been planned for this trial:

1- Upon referring to testing centers at UCSF individuals will receive the trial details via a letter or flyer, and if tested positive for COVID-19, they will contact study staff and enroll into the trial.

2- The UCSF Clinical and Translational Science Institute (CTSI) Participant Recruitment Program (PRP) provides new COVID+ patient lists enabling us to contact COVID+ patient who are interested in participating in research studies.

After study staff confirm their eligibility, participants will receive the sample collection package and written instructions at their home along with scheduling a videoconference to collect saliva samples and use the assigned mouthwash during the 4-week period.

Assignment of interventions: allocation

Sequence generation {16a}

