At any time during the trial, if a participant discontinues from the study or deviates from intervention protocols, we will record the information.

Data management {19}

We have planned to use unique barcodes on sample collection kits and participants' packages to be scanned during the trial and automatically recorded in an Excel file on a UCSF secured laptop and the Cloud. Only PIs know about the codes. [name] (SB) will supervise data entry and its quality on a regular basis. Data will be linked to a REDCap form.

Confidentiality {27}

Email address and telephone number are the only personal identifying information which will be kept confidential in REDCap on UCSF secured servers. Participant information will be kept confidential. After the study and its follow-up in 12 months is finished, email address and phone number will be deleted.

Plans for collection, laboratory evaluation and storage of biological specimens for genetic or molecular analysis in this trial/future use {33}

The study procedures include collecting saliva and oropharyngeal samples from participants on 3 study days (day 1, 7, 28), assaying them, and storing them for future potential research use.

Statistical methods

Statistical methods for primary and secondary outcomes {20a}

Primary outcome measure: To assess and compare the SARS-CoV-2 viral load in unstimulated saliva and throat wash (gargle lavage) samples at baseline, days 7 and 28, we will compare the viral load (cycle threshold, Ct) among active groups versus the control (water) and within groups on day 28 using proportional hazards regression models with right censoring for undetermined Ct, stratifying on replicate for a marginal repeated measures survival model.

We follow the intention-to-treat (ITT) approach for efficacy analyzing participant data asrandomized; a safety analysis will tabulate any adverse experiences. The ITT group will include participants who are randomized after meeting the eligibility criteria and receive at least one study mouthwash dose and have PCR data from collected samples. A safety analysis group will include participants who received study mouthwashes and have safety evaluation data after using the mouthwash at least once.

Interim analyses {21b}

We plan to conduct an interim analysis after 10 participants in each group (N=50) have finished the 28-day period (using mouthwash). The alpha-spending approach with an O'Brien-Fleming stopping rule will be used.

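### The primary analysis in {20a} includes a within-group comparison at day 28, which cannot separate a rinse effect from natural clearance and tests no stated viral-load objective

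*Combined protocol and SAP*

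**What the plan says.** Section {20a} describes the primary analysis in one sentence. Viral load, measured as Ct, is to be compared "among active groups versus the control (water) and within groups on day 28 using proportional hazards regression models", with undetermined Ct treated as right-censored. The two comparisons stand side by side. The within-group one gets no separate alpha, no secondary or descriptive label and no statement of how it will be read. Additional analyses have their own section, {20b}, and it is not placed there.

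The sentence does not say what day 28 is compared with inside a group. Section {12} defines the primary outcome as "Change in RT-PCR SARS-Cov-2 viral load in unstimulated saliva and throat wash (gargle lavage) samples (Time Frame: Baseline to 4 weeks"), so baseline is the natural reading, but it is an inference.

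The study question is between-group throughout. The introduction states: "The null hypothesis of the study is that there is no difference between any OTC antiseptic mouthwash solution" and goes on to list the four rinses and water. Objectives 1a and 1b in {7} are each framed against distilled water. The power statement in {14} concerns "a sample size of 24 for a mouthwash group and 24 for the distilled water control group".

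Three other statements bear on what happens to viral load without an antiseptic:
- The introduction justifies the 4-week period on the ground that "studies show people with COVID can continue to shed the virus and potentially transmit to the others for a 2- to 4-week period".
- Section {10} requires: "Tested positive for COVID-19 with a sample collected in the prior 7 days".
- Section {6b} says that the water control "may help clear microbes from the oral cavity and throat without deactivating SARS-CoV-2 virus".

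**The concern.** A change within one arm from baseline to day 28 mixes at least four things: the natural course of the infection, regression to the mean after selection on a recent positive test, mechanical clearance from gargling any liquid, and any antiseptic effect. Only a comparison with the water arm isolates the last. The within-group test has no such control, yet it carries the primary label.

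Under the plan as written, a product no better than water could be reported as having reduced SARS-CoV-2 load significantly in a primary analysis. Section {14} says the trial is meant to supply effect-size estimates for a definitive trial; an estimate taken from within-arm change would include natural clearance. An interim look is planned at 10 participants per group, and the dissemination section allows early findings to go to a preprint. At that size, within-arm falls may be easier to detect than differences from water.

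**Working it through.** **Timing.** Entry is up to 7 days after the positive sample, so day 28 is roughly 28 to 35 days after it. The shedding period given in the introduction is 2 to 4 weeks, that is 14 to 28 days. Day 28 therefore falls at or beyond the end of that period for most plausible entry times. The plan also expects undetermined Ct values and provides for censoring them.

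**The plan's own figure.** Inputs from {14}: 24 v 24, 80% power, two-sided alpha 0.05, 2-fold difference in means. No SD or CV is given, so the 24 cannot be checked from stated inputs alone. Solving the noncentral t with 46 degrees of freedom and noncentrality d × √(24/2) for 80% power gives d = 0.826. If a 2-fold difference is one log2 unit (an assumption), the implied SD is 1/0.826 = 1.21 log2 units. The retention step reproduces: 24/0.8 = 30 per group, and 30 × 5 = 150.

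**Chance of a significant within-arm fall with no rinse effect.** Approximate the within-arm test by a paired t-test with n = 24 (23 degrees of freedom, critical value 2.069). The SD of change is 1.21 × √(2(1 − r)), where r is the baseline to day 28 correlation (assumed). Noncentrality is (natural fall / SD of change) × √24.

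| r | SD of change | Natural fall | Noncentrality | P(significant fall) |
|---|---|---|---|---|
| 0 | 1.71 | 1 log2 (2-fold) | 2.86 | 78% |
| 0.3 | 1.43 | 1 log2 | 3.42 | 91% |
| 0.5 | 1.21 | 1 log2 | 4.05 | 97% |
| 0 | 1.71 | 2 log2 (4-fold) | 5.72 | >99.9% |

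With a much wider assumed SD of change of 6 Ct:

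| Natural Ct rise | Noncentrality | P(significant fall) |
|---|---|---|
| 2 Ct | 1.63 | 35% |
| 4 Ct | 3.27 | 88% |
| 5 Ct | 4.08 | 97% |
| 8 Ct | 6.53 | >99.9% |

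**All five arms at once.** For five independent arms the probability is the per-arm figure to the fifth power: 0.78^5 ≈ 0.29 in the lowest 2-fold case, and 0.346^5 ≈ 0.005 at an SD of change of 6 Ct with a 2 Ct rise.

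**A check closer to the planned model.** Five identical arms of 24 were simulated with a marginal Cox model on Ct and robust clustered variance. Assumptions: censoring at Ct 40, baseline mean Ct 27, within-person correlation 0.5, 400 runs per scenario, nobody undetectable except through the cut-off at 40.

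| SD (Ct) | Natural rise | Per arm | All five arms |
|---|---|---|---|
| 3 | 2 Ct | 78% | 28% |
| 3 | 3 Ct | 98% | 90% |
| 3 | 5 Ct | 100% | 100% |
| 5 | 2 Ct | 39% | 1% |
| 5 | 3 Ct | 68% | 19% |
| 5 | 5 Ct | 98% | 89% |

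If 30% of participants become undetectable and the others rise by 3 Ct, all five arms are significant in 100% (SD 3) and 98% (SD 5) of runs. In the same simulations, active-versus-water comparisons at day 28 (rank test) rejected in about 4% to 6% of cases in every scenario, as they should with no rinse effect.

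**The case against.** The strongest reply is that the confirmatory question is already between-group. The null hypothesis, the objectives and the sizing all compare rinse with water, and the sentence in {20a} puts that comparison first. Nowhere does the plan say a significant within-arm change will count as efficacy. Water would be analysed within group too, so its fall would be visible beside the others. The trial is a pilot, for which within-arm change is useful planning information. All of this is fair, and it limits the point to the within-group part. It does not explain why a comparison that tests no stated viral-load objective carries the primary label without any limit on interpretation.

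Four stronger readings are tempting, and the documents do not support them:
- **Every arm, water included, will show a significant fall.** The documents give no SD and no natural decline. The chance for all five arms runs from about 0.5% to near certainty across the assumptions above.
- **A false-positive rate near 100%.** If virus truly clears, the within-arm null of no change is false and rejecting it is correct. The error would lie in crediting the fall to the rinse.
- **Shedding ends by 4 weeks.** The introduction says only that "people with COVID can continue to shed the virus and potentially transmit to the others for a 2- to 4-week period", which describes how long shedding can continue, not when it stops.
- **Every favourable result would serve a supporting manufacturer.** One arm is distilled water. The funding section lists support from the makers of the chlorine dioxide, hydrogen peroxide and CPC products, but not from the maker of the essential-oil product.

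**Conclusion.** The point holds for the within-group comparison in {20a} and should be corrected. The size depends on assumptions: the log2 reading of the 2-fold difference, the back-solved SD, the paired t approximation to a censored proportional hazards model, the assumed natural falls and correlations, and baseline as the reference time. Across them, the chance that an arm with no rinse effect shows a significant fall runs from about 35% (2 Ct rise, SD of change 6 Ct) to over 99.9% (4-fold fall at the SD implied by {14}, or 8 Ct at an SD of change of 6 Ct). It would be lower for smaller natural falls. The conclusion that the test cannot isolate a rinse effect follows from its design and does not depend on those figures. The randomised comparison with water remains valid as far as this issue goes, so the defect is one of labelling and interpretation, not of the trial's main contrast.

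**What to change.** In {20a}:
- Remove the within-group comparison from the primary analysis sentence.
- State that viral-load conclusions for objectives 1a and 1b rest only on the active-versus-water contrast.
- Report within-arm change from baseline, with baseline named as the reference, as an estimate and confidence interval without a p-value. Show the water arm's change beside each active arm.

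The cost is a small change of wording, with no extra data or participants. The within-arm p-values are lost, but the descriptive information useful for planning a later trial is kept.

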The four OTC alcohol-free, fluoride-free, gluten-free mouthwash intervention groups are as follows: Chlorine Dioxide (ClO₂) (CloSYS Ultra Sensitive, Rowpar Pharmaceutical Inc., USA); Hydrogen Peroxide (H₂O₂) (Oral-B Mouth Sore, Proctor & Gamble, USA); Cetylprydinium Chloride (CPC) (Crest Pro-Health Multi-Protection, Proctor & Gamble, USA); Essential Oils (EO) (Listerine Zero, Johnson & Johnson, USA), which were selected based on being OTC alcohol-free and fluoride-free products legally marketed in the US, each with a different main active ingredient. Participants will be asked to rinse and gargle for 30-60 seconds with 10-20 ml (2-4 teaspoons) of the assigned mouthwash 4 times per day (including after each meal and before bedtime), for 4 weeks.

Criteria for discontinuing or modifying allocated interventions {11b}

In the rare case that a study participant has an adverse experience possibly, probably, or definitely related to the assigned oral rinse, he or she will be instructed to discontinue using the rinse to see if the problem resolves. At the discretion of the participant and investigators, after a problem resolves, the participant may resume using the rinse. If the problem does not resolve, the participant will be instructed to not resume using the rinse; if possible, the participant will be encouraged to still provide the follow-up samples and report symptoms. If a participant's clinical symptoms worsen, he or she will be instructed to contact his or her primary care physician to get

the required medical care for his or her health. A participant can withdraw him- or herself at any time without concern for repercussions about their health care.

Strategies to improve adherence to interventions {11c}

During the study, adherence data will be collected through a daily REDCap questionnaire distributed via SMS text message, asking about the frequency and duration of mouthwash use, as well as clinical symptoms and healthcare utilization.

Relevant concomitant care permitted or prohibited during the trial {11d}

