The permuted block allocation sequence stratified on language (English/Spanish) will be generated in SAS and uploaded to REDCap to randomly assign participants to one of the five mouthwash groups.

Concealment mechanism {16b}

The randomization will be concealed in REDCap; once participant's eligibility is confirmed, consent form is signed, and the baseline questionnaire completed, then the assignment is revealed. No study staff involved in recruitment or procedures with participants or participants know the allocation sequence since it is revealed via REDCap after qualifying steps.

Implementation {16c}

Following release of the REDCap allocation sequence for an individual participant, study staff will obtain the relevant kit and deliver to participants.

Assignment of interventions: Blinding

Who will be blinded {17a}

Participants will be blinded/masked to the extent possible by covering product labels, but the solutions have different colors, flavors, and smells so they may guess which group they have been assigned. Lab staff performing assays (outcome assessors) and data analysts will be blinded/masked to intervention group.

Lab staff will receive participants' samples with barcode stickers with only the study ID number. The data analyst will receive data set with coded group identifier.

Procedure for unblinding if needed {17b}

We will not unblind the study groups for outcome assessors unless subsequent actions to assure participants' safety would be affected.

Data collection and management

Data will be collected via various questionnaires (eligibility, baseline, daily and long-term follow ups) designed in REDCap. The data collection will be supervised and assessed regularly for completeness and inconsistencies.

Plans for assessment and collection of outcomes {18a}

We have designed questionnaires (eligibility, baseline, daily and long-term follow ups, sample collection, and RT-PCR results) in REDCap to collect data from participants and assess outcomes. We will train research and lab staff regarding each related steps and data collection. We have pilot tested assessments. The data collection will be supervised and assessed regularly for discrepancies.

Plans to promote participant retention and complete follow-up {18b}

We have planned to send daily reminders to participants to use their assigned mouthwashes and follow-up the next day to see if they have used it and if there were problems.

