Methods for additional analyses (e.g. subgroup analyses) {20b}

Similar proportional hazards regression analyses will be conducted for baseline (after rinse) and day 7. We will assess the relationship between study results and baseline variables (demographics, clinical symptoms, tobacco use, etc.).

Methods in analysis to handle protocol non-adherence and any statistical methods to handle missing data {20c}

Since PCR Ct data (inversely proportional to viral load) are expected to include right censored data when the assay is stopped before sufficient amplified viral genetic material is detected, we plan to use statistical analyses which can accommodate right censoring. Alternatively, we may use multiple imputation for Ct values above the detection level (e.g. 32, 35, or 40) and combine the estimates and variability across multiple imputations.

Plans to give access to the full protocol, participant level-data and statistical code {31c}

We will make the protocol available as per ClinicalTrials.Gov requirements. We do not plan to provide access to participant-level data. We may make statistical code available with publications.

Oversight and monitoring

Composition of the coordinating center and trial steering committee {5d}

SG, study PI and supervisor, and SB, co-PI form the steering committee. They will have regular weekly meetings to review and supervise various study steps and train/lead study staff. They will work with different study staff groups (e.g. recruitment, data management, and lab staff) on a

regular basis to assess trial steps and solve any problems/errors that might rise.

Composition of the data monitoring committee, its role and reporting structure {21a}

SG, the PI, is a biostatistician and clinical trialist who will instruct and supervise study staff on designing questionnaires, data collection, and data analyses. SB, the co-PI, is a dental clinician who will work closely with and report to SG.

Adverse event reporting and harms {22}

REDCap will be configured with Twilio to send a daily text message to participants with a link to a very short REDCap questionnaire asking about previous day mouthwash use and possible adverse experiences.

Frequency and plans for auditing trial conduct {23}

Study PIs will audit trial conduct and trial procedures weekly to resolve possible errors and make decisions about required modifications, staff re-training, etc.

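### The daily text is the only active source of adverse experiences the plan names, appears to look back one day, and has no stated catch-up, so short or reply-stopping events can be under-counted

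*Combined protocol and SAP*

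**What the plan says.** All references are to the combined protocol and SAP.

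- Section {22} names one way of collecting adverse experiences: a daily text with a link to a very short questionnaire "asking about previous day mouthwash use and possible adverse experiences".
- Section {18b} describes daily reminders and a "follow-up the next day to see if they have used it and if there were problems".
- Section {11c} describes a daily questionnaire sent by text "asking about the frequency and duration of mouthwash use, as well as clinical symptoms and healthcare utilization". Adverse experiences are not in that list.
- Section {11b} says that a participant with a possibly related adverse experience stops the rinse: "he or she will be instructed to discontinue using the rinse to see if the problem resolves". If the problem persists, "the participant will be encouraged to still provide the follow-up samples and report symptoms" where possible.
- Section {30} offers study phone numbers and email addresses for problems during the study. It also provides a roughly quarterly questionnaire once the intervention has ended, with this period and content: "next 11 months to see how they are doing, their clinical symptoms, acceptability of using the assigned mouthwash during the trial". Possible later use is asked as well. Section {13} adds healthcare utilization to this later contact.
- Section {20a} tabulates adverse experiences. The safety group is limited to those who received a study mouthwash and "have safety evaluation data after using the mouthwash at least once".
- Section {12} makes symptoms and healthcare utilization, including hospitalization, secondary outcomes from baseline to 4 weeks.

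**The concern.** If each form covers only the day before it, an unanswered form leaves a gap that the next form does not fill. Nothing in {22}, {18b} or {11c} says that a missed day is asked about later. Section {33} describes days 7 and 28 as sampling days, and no section adds a cumulative safety or healthcare question to them. The missing-data section {20c} deals only with Ct values.

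The gap matters most when the event causes the silence. Participants are infected adults at home, and someone who is admitted, very ill or put off by a reaction is less likely to answer a text. The missing reports are then informative, and counts of adverse experiences and admissions would tend to be too low. Section {17a} notes that the solutions differ in color, flavor and smell, so reply rates could differ by arm. If they did, the comparison with water would be biased. The documents neither show nor exclude such a difference.

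**Working it through.** **Plan's own figure.** There is none: the documents give no daily reply rate and no expected capture of adverse experiences. The reply rates below are assumptions.

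**Inputs.** Daily forms over the 4-week period: 28. Assumed reply rate p = 0.90, 0.80, 0.60, so the probability of an unanswered form is q = 1 − p = 0.10, 0.20, 0.40. Misses are taken as independent from day to day.

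**Previous-day look-back.** An event lasting L days is touched by L forms and is lost only if all L go unanswered: P(missed) = q^L. Expected unanswered forms per participant = 28q.

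| Reply rate | Unanswered forms of 28 | L = 1 | L = 2 | L = 3 |
|---|---|---|---|---|
| 90% | 28 × 0.10 = 2.8 | 10% | 0.10² = 1% | 0.10³ = 0.1% |
| 80% | 28 × 0.20 = 5.6 | 20% | 0.20² = 4% | 0.20³ = 0.8% |
| 60% | 28 × 0.40 = 11.2 | 40% | 0.40² = 16% | 0.40³ = 6.4% |

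Under independence the loss falls mainly on events of one or two days.

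**Look-back to the last completed report.** A one-day event is lost only if the form covering it and every later form go unanswered. With the event equally likely on any of the 28 days, P(missed) = (1/28) × Σ q^k for k = 1 to 28, which is very nearly q / [28(1 − q)]:

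- 90% reply: 0.10 / (28 × 0.90) = 0.4%, against 10%.
- 80% reply: 0.20 / (28 × 0.80) = 0.9%, against 20%.
- 60% reply: 0.40 / (28 × 0.60) = 2.4%, against 40%.

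**Dependent misses.** The q^L figures do not hold when the event itself stops the replies. In the limiting case, a three-day admission that leaves all three of its forms unanswered is lost to the daily form entirely under a previous-day look-back, whatever the usual reply rate. A look-back to the last completed report recovers it once the participant answers again.

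**Content of the daily form.** Section {11c} lists frequency and duration of use, symptoms and healthcare utilization. Section {22} lists mouthwash use and adverse experiences. If this is one form, the two lists differ and neither is complete.

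**The case against.** The case on the other side has several sound parts.

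- In {22} the words about the previous day may limit only mouthwash use, and {11c} gives no look-back for symptoms or healthcare utilization. The REDCap items are not in the documents. This stands, which is why the one-day look-back is described as apparent. The next-day check on problems in {18b} makes it the more natural reading, and if the window is open, {22} still needs to state it.
- A reader might infer that an event on an unanswered day is never asked about again. The documents do not say so. They are silent on re-asking, a lasting event would be caught by a later form, data are checked regularly for completeness, {18b} records discontinuations and deviations, {23} provides a weekly audit, and participants can call or email. None of these is a stated re-query of a missed form, and calling depends on the participant.
- A reader might infer that problems open at day 28 are not followed. That is too strong. Section {11b} watches for resolution, and the later questionnaires ask about symptoms, healthcare utilization and mouthwash experience. They do not name adverse experiences or state a look-back to the 4 weeks, so what is missing is a defined adverse-event follow-up.
- A reader might infer that someone who reacts to the first dose drops out of the safety group. Objective 1a and {15} suggest that the first rinse is used during a staff videoconference, so an immediate reaction could well be seen.
- The 80% retention in {14} is a sample-size assumption through day 28. It is not a daily reply rate and cannot be used as one.

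A daily prompt plus contact details is a reasonable base for a pilot of over-the-counter rinses.

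**Conclusion.** The point holds as a gap in what the plan states. The daily text is the only active source of adverse experiences named; it appears to look back one day; and no catch-up, cumulative day 7 or day 28 question, or defined adverse-event follow-up after day 28 is given. The safety table and the hospitalization outcome are exposed to under-counting of short events and of events that stop replies.

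With reply rates of 90% to 60%, a one-day event is missed 10% to 40% of the time and a three-day event 0.1% to 6.4%. These figures rest on assumed reply rates, independence and the one-day reading. Event-driven silence would raise them by an amount the documents do not allow to be estimated. Bias between arms is possible but conditional on reply rates differing. This is a worthwhile, low-cost improvement to the collection of harms and secondary outcomes; it does not touch the viral-load measurements.

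**What to change.** 1. In {22}, {11c} and {18b}, word the adverse-experience, symptom and healthcare items as covering the time since the last completed report, with event dates. Mouthwash use can remain a previous-day item.
2. Repeat those items cumulatively at the day 7 and day 28 sample contacts.
3. Add two items to the first 3-monthly questionnaire: any hospital admission during the 4 weeks, with its date; and any rinse-related problem that was unresolved at day 28 or is new.
4. In {20a}, report by arm the number who used the rinse but gave no safety data.
5. Reconcile the daily-form content listed in {11c} and {22}.

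The cost is small: existing REDCap items are reworded and a few questions are added at contacts already planned. The downside is slightly longer recall after a missed day and a slightly longer questionnaire. No treatment rule changes.
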